If the patient is seen for treatment outside the protocol (routine care) or for any emergency, the investigator shall collect all the information relevant to the trial (date of consultation, reason for consultation, occurrence of AEs, etc.).

V3 — Clinical follow-up visit at 6 months (± 1 month) — Standard practice

- **Clinical examination**: Verification of the functional status of the treated tooth and percussion test (lateral and axial),
- Recording of AEs.
- Retro-alveolar X-ray check to evaluate the results of endodontic treatment at 6 months: 1) density of the root canal filling (radiopacity + presence of voids), 2) progress of resorption of the extruded material

where appropriate, **3)** apical lesion (absence/appearance/still present compared with T0) and progress of the size of an existing lesion (reduction, stabilization or increase).

Upload the 6-month follow-up retro-alveolar image to the eCRF (reminder: the entire tooth – from the *crown to the apex, including the root* – must be visible in the image; see chapter 6.1).

— The investigator shall evaluate the efficacy of the endodontic treatment on the basis of the clinical and radiological criteria identified (*Note: Only the evaluation of the radiological criteria by the independent reviewers will be taken into account for the primary evaluation criterion (PEC); the investigator's evaluation is to be used to determine further clinical follow-up*).

Procedure in the event of the appearance of a lesion or an increase in the size of a pre-existing lesion:

- If the investigator considers it to be an emergency (e.g. if the tooth is symptomatic and/or non-functional): the investigator will notify the patient of the failure of the endodontic treatment and schedule retreatment. In this case, the patient leaves the trial early due to the failure of the treatment and continues endodontic treatment outside the trial (end-of-trial form to be completed in the eCRF). Performance and safety evaluations now end. Failure notified at 6 months is carried forward as the PEC value (response at 24 months = failure). The patient will not be replaced.
- If the investigator considers that it is NOT an emergency (e.g. if the tooth is asymptomatic): medical advice should be sought from the trial coordinator (who will review the X-rays) before considering retreatment and early discharge from the trial for treatment failure.

V4 — Clinical follow-up visit at 12 months (± 1 month) — Standard practice

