- **Clinical examination**: verification of the functional status of the treated tooth and percussion test (lateral and axial),
- Recording of AEs.
- **Retro-alveolar X-ray check** to evaluate the results of endodontic treatment at 12 months: 1) density of the root canal filling (radiopacity + presence of voids), 2) progress of resorption of the extruded material where appropriate, 3) apical lesion (absence/appearance/still present compared with T0) and progress of the size of an existing lesion (reduction, stabilization or increase).

Upload the 12-month follow-up retro-alveolar image to the eCRF (reminder: the entire tooth – from the *crown to the apex, including the root* – must be visible in the image; see Chapter 6.1).

— The investigator will evaluate the efficacy of the endodontic treatment on the basis of the clinical and radiological criteria identified (*Note: Only the evaluation of the radiological criteria by the independent reviewers will be taken into account for the primary evaluation criterion (PEC); the investigator's evaluation will be used to determine further clinical follow-up*).

Procedure in the event of the appearance of a lesion or an increase in the size of a pre-existing lesion:

- If the investigator considers it to be an emergency (e.g. if the tooth is symptomatic and/or non-functional): the investigator will notify the patient of the failure of the endodontic treatment and schedule retreatment. In this case, the patient leaves the trial early due to the failure of the treatment and continues endodontic treatment outside the trial (end-of-trial form to be completed in the eCRF). Performance and safety evaluations now end. Failure notified at 12 months is carried forward as the PEC value (response at 24 months = failure). The patient will not be replaced.
- If the investigator considers that it is NOT an emergency (e.g. if the tooth is asymptomatic): medical advice should be sought from the trial coordinator (who will review the X-rays) before considering retreatment and early discharge from the trial for treatment failure.

V5 — Clinical follow-up visit at 24 months (± 1 month) — Standard practice

- **Clinical examination**: verification of the functional status of the treated tooth and percussion test (lateral and axial),
- Recording of AEs.

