- **Retro-alveolar X-ray check** to evaluate the results of endodontic treatment at 24 months: 1) density of the root canal filling (radiopacity + presence of voids), 2) progress of resorption of the extruded material where appropriate, 3) apical lesion (absence/appearance/still present compared with TO) and progress of the size of an existing lesion (reduction, stabilization or increase).

Upload the 24-month follow-up retro-alveolar image to the eCRF (reminder: the entire tooth – from the *crown to the apex, including the root* – must be visible in the image; see Chapter 6.1).

— Where appropriate (in the event of the appearance of a lesion or an increase in the size of a pre-existing lesion), notification of ET failure by the investigator: schedule retreatment.

For patients in the PA1704 group whose endodontic treatment is effective at 24 months: Offer to continue clinical follow-up for up to 5 years: Inform patients about the study (dedicated information note) and provide them with a consent form.

— Complete the end-of-study form at the end of the eCRF for patients whose clinical follow-up has been completed (all patients in the BioRoot™ RCS group are followed-up with for up to 24 months, and patients in the PA1704 group who decline to continue the clinical follow-up for up to 5 years or for whom treatment failure is notified at 24 months).

PA1704 arm: V6 — Clinical follow-up visit at 3.5 years (± 6 months) — Standard practice

- **Clinical examination**: Verification of the functional status of the treated tooth and percussion test (lateral and axial),
- Recording of AEs.
- **Retro-alveolar X-ray check** to evaluate the results of endodontic treatment at 3.5 years: 1) density of the root canal filling (radiopacity + presence of voids), 2) progress of resorption of the extruded material where appropriate, 3) apical lesion (absence/appearance/still present compared with T0) and progress of the size of an existing lesion (reduction, stabilization or increase).

Upload the 3.5-year follow-up retro-alveolar image to the eCRF (Reminder: The entire tooth – from the *crown to the apex, including the root* – must be visible in the image; refer to Chapter 6.1).

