— The investigator will evaluate the efficacy of the endodontic treatment on the basis of the clinical and radiological criteria identified (*Note: Only the evaluation of the radiological criteria by the independent reviewers will be taken into account for the primary evaluation criterion (PEC); the investigator's evaluation will be used to determine further clinical follow-up*).

Procedure in the event of the appearance of a lesion or an increase in the size of a pre-existing lesion:

- If the investigator considers it to be an emergency (e.g. if the tooth is symptomatic and/or non-functional): the investigator will notify the patient of the failure of the endodontic treatment and schedule retreatment. In this case, the patient leaves the trial early due to the failure of the treatment and continues endodontic treatment outside the trial (end-of-trial form to be completed in the eCRF). Performance and safety evaluations now end.
- If the investigator considers that it is NOT an emergency (e.g. if the tooth is asymptomatic): medical advice should be sought from the trial coordinator (who will review the X-rays) before considering retreatment and early discharge from the trial for treatment failure.

PA1704 arm: V7 — Clinical follow-up visit at 5 years (± 6 months) — Standard practice

— **Clinical examination**: Verification of the functional status of the treated tooth and percussion test (lateral and axial),

- Recording of **AEs**.
- **Retro-alveolar X-ray check** to evaluate the results of endodontic treatment at 5 years: 1) density of the root canal filling (radiopacity + presence of voids), 2) progress of resorption of the extruded material where appropriate, 3) apical lesion (absence/appearance/still present compared with T0) and progress of the size of an existing lesion (reduction, stabilization or increase).

Upload the 3.5-year follow-up retro-alveolar image to the eCRF (Reminder: The entire tooth – from the *crown to the apex, including the root* – must be visible in the image; refer to Chapter 6.1).

- The investigator will evaluate the efficacy of the endodontic treatment on the basis of the clinical and radiological criteria identified (*Note: Only the evaluation of the radiological criteria by the independent reviewers will be taken into account for the primary evaluation criterion (PEC); the investigator's evaluation will be used to determine further clinical follow-up*).

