7.7. Statistical methods

The statistical methods are based on the following elements and will be detailed in the Statistical Analysis Plan.

7.7.1. Sample description:

The description of the subjects enrolled who completed the trial and those enrolled who left prematurely will be presented using a table of absolute (N) and relative (%) frequency. Reasons for premature discharge and deviations from the protocol will be listed.

7.7.2. Descriptive analyses:

Clinical data collected at enrolment and at each visit will be described. Descriptive statistics will be presented according to the nature of the criterion analyzed:

- Quantitative variable: sample size, number of missing data sets, mean, standard deviation, median, minimum and maximum;
- Qualitative variable: absolute frequencies (N) and relative frequencies (%) per class in each group, number of missing data.

Graphs will be provided for each variable.

7.7.3. Comparative analyses:

A comparison of 2 independent means will be made using the Student's t-test; if the variances are unequal (verified by the Fisher's test), use the Welch's test instead of the Student's test. If the conditions for applying the Student test are not met (n < 30), the non-parametric Wilcoxon test is used.

2 independent percentages are compared using Pearson's Chi-2 test. If the conditions for application are not met (at least one theoretical number < 5), Fisher's exact test is used.

7.7.4. Analysis of primary performance criterion:

As a reminder, the primary performance criterion is the efficacy rate at 24 months of treatment based on clinical criteria assessed by the investigator (tooth functionality and pain level) AND radiological criteria assessed blind by independent reviewers (complete healing, reduction of lesions, failure). In the event of failure at 6 or 12 months, the patient will be considered to have failed at 24 months.

The primary criterion will be analyzed using 2 approaches, in accordance with the literature:

- **Primary analysis of soft criteria**: treatment rates with complete or incomplete cure are compared against failure rates;
- **Secondary analysis of strict criteria**: treatment rates with complete healing are compared against rates of failure or incomplete healing (complete healing can take up to 4 or 5 years).

The comparison of efficacy rates between the 2 groups will be carried out using the Dunnett and Gent χ^2 test (Dunnett CW and Gent M 1977; Elie C et al 2008).

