Maximum pain in the first 7 days and time to onset of maximum pain: Description and comparison, between the PA1704 arm and the BioRoot™ RCS arm, of the maximum pain experienced during the 7 post-operative days and its time to onset by a Student, Welch or Wilcoxon test.

Intra-operative pain relief between T0 and D7: Description of painkiller classes, reasons for use, frequency of use and cumulative dose per patient over 7 days. Description and comparison, between the PA1704 arm and the BioRoot™ RCS arm, of the proportion of patients who used *oral* pain medication between T0 and D7 by Pearson's Chi-2 test or Fisher's exact test.

Description of the surgical technique: Description and comparison, between the PA1704 arm and the BioRoot™ RCS arm, of the type of anesthesia, the technique used to remove the old filling material (if root canal re-treatment only), the technique used to shape the canal, the type of disinfectant and rinse solutions used and irrigation techniques, the method of application of filling material and gutta-percha condensation, and the coronal restoration technique, by Pearson's Chi-squared test or Fisher's exact test. Intraoperative complications will be described where appropriate.

Operator comfort and satisfaction: Description and comparison, between the PA1704 arm and the BioRoot™ RCS arm, of operator comfort criteria. Satisfaction will be described at T0 and 2 years, and the proportions of satisfied operators will be compared.

For the performance criteria (efficacy rate, filling density, and material resorption) evaluated at 3.5 years and 5 years in the PA1704 arm: These criteria will only be described.

7.7.6. Safety/tolerance analysis:

The tolerance analysis will focus on the Tolerance population. Tolerance data is to be expressed as the number of adverse events (AEs) and the number of patients reporting at least one AE. Severity, cause (filling material or surgical technique) and the time of occurrence shall be described. The proportions of AEs and patients with AEs will be compared between the 2 groups. The proportions of patients who used an additional dental consultation for significant post-operative complication or pain will be described and compared, between the PA1704 arm and the BioRoot™ RCS arm, by Pearson's Chi-squared test or Fisher's exact test.

Defects in the devices will be described in the form of a list and proportions will be compared between the 2 groups.

7.7.7. Intermediate analyses:

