No interim analysis of the primary criterion is planned. The main analysis will only be carried out after the 2-year follow-up of all patients enrolled.

Two interim analyses of the secondary criteria have been planned. These will be carried out after 6 and 12 months' follow-up for all included patients.

The alpha risk will not be inflated, as the main criterion will not be analyzed in the interim analyses. Therefore, no alpha risk adjustment method is required. The final analysis will focus on the primary and secondary criteria.

For patients treated with the PA1704 ready-to-use filling material and who agree to be followed-up with for up to 5 years, a non-comparative descriptive analysis of secondary performance and safety criteria at 3.5 years and 5 years will be carried out at the end of their participation.

7.7.8. Criteria for stopping the clinical trial from a statistical point of view:

None. Interim analyses are only used to collect data on secondary criteria before the end of the study. The conclusion on the non-inferiority of PA1704 compared to BioRoot™ RCS will only be made on the final analysis at 2 years.

7.7.9. Changes to the statistical analysis plan:

The statistical analysis plan will be drawn up before the first interim analysis is carried out. The initial analysis strategy may undergo minor modifications following each data review, and the new statistical analysis plan will be described in detail at that time.

7.7.10. Specification of sub-groups for further analysis:

The following sub-group analyses will be carried out, at least on the PP population, during the final analysis at 2 years. Other factors not considered in this protocol may be added in the Statistical Analysis Plan.

- For the primary criterion, the rate of effective treatment at 2 years:
 - Prognostic factors at enrolment
 - Presence or absence of a periapical lesion,
 - Indication for endodontic treatment: initial versus repeat endodontic treatment,
 - Factors related to the surgical procedure
 - Type of rinse solution used to finalize root canal disinfection,
 - Operating techniques used: technical platform used (whether or not a microscope was used), manual files versus continuous rotation versus alternative rotation.
- Post-operative pain:
 - Operating techniques used: manual files versus continuous rotation versus alternative rotation.
 - Initial pulp pathology (pre-existing inflammatory situation or necrosis or live pulp),

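### As written, the 3.5- and 5-year PA1704 efficacy rates describe only patients who continued after success at 24 months, and omit failures that have already left, unless the later SAP sets another denominator

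*Combined protocol and SAP*

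**What the plan says.** **Who enters.** Section 6.5.2 (V5) reads: "For patients in the PA1704 group whose endodontic treatment is effective at 24 months: Offer to continue clinical follow-up for up to 5 years". The same visit completes the end-of-study form for PA1704 patients who decline "or for whom treatment failure is notified at 24 months".

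**Failures before 24 months.** For a failure sent to retreatment at V3 the text is "Failure notified at 6 months is carried forward as the PEC value (response at 24 months = failure"); at V4 it is "Failure notified at 12 months is carried forward as the PEC value (response at 24 months = failure"). Section 7.7.4 repeats the rule: "In the event of failure at 6 or 12 months, the patient will be considered to have failed at 24 months". Section 7.7.11 plans no other imputation.

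**Failures after 24 months.** Under section 6.3, a failure needing retreatment ends participation in the PA1704 arm at any time before the 5-year visit. The V6 text says "Performance and safety evaluations now end". Unlike V3 and V4, it gives no value for the later visit.

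**Analysis.** Table 3 (section 6.1) lists 3.5- and 5-year efficacy rates for the PA1704 arm. Section 7.7.5 says of the performance criteria "evaluated at 3.5 years and 5 years in the PA1704 arm: These criteria will only be described". Section 7.7.7 plans, for PA1704 patients "who agree to be followed-up with for up to 5 years, a non-comparative descriptive analysis of secondary performance and safety criteria". No denominator is stated. Section 7.7 leaves detail to a later SAP, and section 7.7.1 will list reasons for leaving early.

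**Another wording of the offer.** The synopsis (section 2.1) and the opening of section 6.5.2 offer the two extra visits to PA1704 patients with no condition of success.

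**The concern.** A reader will take a 5-year efficacy rate to mean the share of treated teeth that are effective at 5 years. The plan as written gives something narrower: the share still effective among patients who had succeeded at 24 months, agreed to go on and were still being followed. The failures recorded as exits are in neither the numerator nor the denominator. Listing the reasons for leaving makes these exits visible but does not put them in the rate.

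Section 3.4 ties the long-term data to the CE-marking application and to the 5-year life span claimed for the comparator. A figure that appears to hold steady or improve after 24 months could be read there as durability when it partly reflects who was kept in.

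**Working it through.** **1. The plan's own figures.** Section 7.2 assumes 90% efficacy at 24 months in both arms, a 13-point margin, one-sided 5% and, with section 7.3, 80% power. Then n = (1.645 + 0.842)² × 2 × 0.90 × 0.10 / 0.13² = 65.9, so 66 per arm, as stated. Adding 20% gives 66 × 1.2 = 79.2, so 80, as stated. The documents give no expected figure for 3.5 or 5 years.

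**2. Formulas.** Let p = efficacy at 24 months (0.90). Let c = share of these still effective at 5 years (assumed). Let f = share of 24-month failures that enter the extension and still read as failed (assumed, with equal uptake).
- Rate among continuers = p·c / (p + (1 − p)·f)
- Rate from T0 = p·c

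The share f can exceed zero because the investigator notifies failure at V5, while the central reading of the 24-month images follows all the visits (section 6.1). Failures seen only by the readers can therefore enter.

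**3. Results at p = 0.90, c = 0.95.** The rate from T0 is 0.90 × 0.95 = 85.5%.

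| f | Among continuers | Gap (points) |
|---|---|---|
| 0 | 0.855 / 0.90 = 95.0% | 9.5 |
| 0.3 | 0.855 / 0.93 = 91.9% | 6.4 |
| 0.5 | 0.855 / 0.95 = 90.0% | 4.5 |

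In every row the continuers' rate is at or above the 24-month 90%, although the share of all teeth has fallen to 85.5%. With c from 0.90 to 0.97 and f from 0 to 0.5, the gap runs from 4.3 to 9.7 points.

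**4. Other 24-month rates.** Section 3.1.2 cites 85.2% (initial treatment) and 77.2% (retreatment). With c = 0.95 and f = 0, the gap is 0.95 × (1 − 0.852) = 14.1 points and 0.95 × (1 − 0.772) = 21.7 points.

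**5. In counts.** Of 66 evaluable, about 59 are effective and 7 have failed. If 56 stay effective, the rate is 56/59 = 94.9% with no failure entering, 56/62 = 90.3% with 3 entering, and 56/66 = 84.8% from T0.

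**6. Exits after 24 months.** If half of the later failures (2.5% of continuers) leave before V7 and f = 0, the rate among those seen at V7 is 0.95 / 0.975 = 97.4%, still against 85.5% from T0. The documents do not fix how many would leave.

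**7. What a rate from T0 must do** (target 85.5%).
- Count exits at any time: 0.90 × 0.975 × (0.95 / 0.975) = 85.5%.
- If exits are counted only at scheduled visits, those between V6 and V7 drop out. With half of the later failures leaving then, the result is 0.90 × 0.974 = 87.7%; with all of them, 0.90 × 1 = 90%.
- A crude proportion, adding all earlier failures to those who continued, is too low when patients decline. With 30% declining at random and f = 0, it is (0.70 × 0.855) / (0.70 × 0.90 + 0.10) = 0.5985 / 0.73 = 82.0%.
- Multiplying the 24-month efficacy rate by the later rate counts reader-only failures twice. At f = 0.3 it gives 0.90 × 0.919 = 82.7%.

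**8. Lower bounds.** With the 80 − 66 = 14 losses by 24 months taken as failures, the figure is (66/80) × 0.855 = 70.5%. If 30% of those eligible also decline and all of them count as failures, it is 0.705 × 0.70 = 49.4%.

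**The case against.** The strongest reply is that these are secondary, single-arm, descriptive results with no test or decision rule. The plan states the success condition at V5 and names the analysed patients as those who agree to continue. Exits are listed, the 24-month rate will be reported alongside, and a later SAP may define the denominator. The synopsis also offers the visits to all PA1704 patients.

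Much of this stands, and it limits the weight of the point. It does not remove it. The SAP is to build on these elements, and they set no denominator. Under the broader offer, failures needing retreatment still leave under section 6.3.

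A reader might infer more than the documents support:
- *That the non-inferiority result is compromised.* It is not. Failures at 6 and 12 months are carried into the 24-month endpoint, and the extension begins after it.
- *That every failure is excluded, so the bias is 9.5 points.* Reader-only failures can enter. At V3, V4 and V6, failures not judged urgent go to the coordinator before any exit.
- *That 9.5 points is a ceiling.* It holds only at 90% and 95% retention; lower 24-month rates give larger gaps.
- *That the protocol fixes a continuers-only denominator.* It leaves the denominator open.

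**Conclusion.** The point holds for the long-term secondary results. Followed as written, and unless the later SAP says otherwise, the plan yields 3.5- and 5-year rates conditional on success at 24 months and on agreeing to continue, without the failures that left at 6, 12 or 24 months or later. At the protocol's 90% the illustrative gap is 9.5 points, falling to 6.4 or 4.5 if some failures enter. Retention and entry shares are assumptions, and the calculation treats decliners and losses as similar to those followed. Section 3.1.2 puts that in doubt, since it reports that absent patients had more symptoms and felt that treatment had failed.

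Two ambiguities add to this. Exits are notified by the investigator, while efficacy status uses the central readers' radiology. A tooth can thus be an exit for failure yet effective in the 24-month rate, or the reverse. In addition, teeth of uncertain efficacy (Table 4) count with effective ones in the main analysis, but the V5 text does not say whether they are offered the visits.

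**What to change.** In sections 7.7.5, 7.7.7 and 7.7.11:

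1. Label the continuers-only rate *among PA1704 patients effective at 24 months who continued*, with the numbers offered, declined, lost and exited for failure.
2. Beside it, report a rate from T0. Keep as a failure at all later time points every failure that led to exit, retreatment or no offer of V6/V7, at any time from T0 to V7 and not only at scheduled visits. Use a method that handles decliners and losses, such as a life-table estimate of failure exits combined with status at the visit among those still followed. Do not use a crude proportion.
3. State that exits are investigator-notified while efficacy status uses the readers' radiology, so this rate may differ from the 24-month efficacy rate in either direction. State how uncertain teeth that are not followed are counted.
4. State the assumption that decliners and losses resemble those followed. Give the figure with both counted as failures as a lower bound only.

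Separately, reconcile the synopsis, the opening of section 6.5.2 and the V5 text on who is offered V6/V7, including uncertain teeth. This point does not say which rule applies.

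The cost is a few sentences and one more descriptive rate from data already recorded. The long-term figure will be less favourable, and reconciling the offer may need a protocol amendment.
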